7.3.3.5 Recurrence of LDH

Recurrence of LDH is defined as below:

A subject who has all of the following conditions:

- a. The subject shows improvement according to all of the following clinical symptoms at Week 13:
 - Reduction of $\geq 30\%$ in worst leg pain score from baseline,
 - Improvement of $\geq 30\%$ in ODI score from baseline, and
 - Maintenance or improvement of neurologic status (motor, sensory, reflexes) from baseline.
- b. At week 52:
 - Subject does NOT have reduction of $\geq 30\%$ in worst leg pain score from baseline,

- Subject does NOT have improvement of $\geq 30\%$ in ODI score from baseline, and
- Maintenance of or experiences worsening of neurologic status (motor, sensory, reflexes) from baseline.

Percentages will be reported out of subjects with any Week 52 data. If a subject has missing values, they will be imputed as negative outcomes (for example, missing leg pain will be interpreted as not having 30% reduction).

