5.3 Post-treatment Surgery Follow-up for Withdrawn Subjects

Subjects withdrawn from the study will be followed by investigators until 52 weeks after injection to gather data about post-treatment surgery. Information about post-treatment

surgery will be collected for following surgery types:

- Post-treatment surgery for treatment of LDH at the same level of administration of the investigational product;
- Post-treatment surgery for treatment of LDH at a different level than administration of the investigational product; and
- Post-treatment lumbar surgery not for treatment of LDH.

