- ii. Poor response to investigational product that leads the investigator to judge it necessary to perform a surgical intervention for back pain/leg pain or withdraw from the study
- iii. Increase of measurement value on either vertebral body angle formed by flexion or vertebral body translation from baseline to values:
 - Vertebral body angle formed by flexion of $\geq 5^\circ$, or

- Vertebral body translation of ≥ 3 mm
- iv. Occurrence of treatment-related AEs that lead the investigator to judge it necessary for the subject to have surgical intervention or withdraw from the study

*2 Recurrence of LDH is defined as below:

A subject who has all of the following conditions:

- a. The subject shows improvement according to all of the following clinical symptoms at Week 13:
 - Reduction of 30% in worst leg pain score from baseline,
 - Improvement of 30% in ODI score from baseline, and
 - Maintenance or improvement of neurologic status (motor, sensory, reflexes) from baseline;
- b. The subject does not show with any improvement of worst leg pain score, ODI score, or neurologic status at Week 52 or discontinuation visit; and
- c. The subject has been judged by the investigator as a “Treatment Failure” for efficacy reason⁽ⁱⁱ⁾, as described above.

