9.5.12 Post-treatment Surgery for Lumbar Disc Herniation at Target Level

- Assessment Point: Week 52 (subjects who discontinued the study will be also followed until 52 weeks after injection)
- Item: Occurrence of lumbar disc surgery for LDH [Yes, No], Date of surgery
- Method: At 52 weeks after injection, investigators will collect information on the occurrence of post-treatment surgery for treatment of LDH at the same level of administration of the investigational product, including for subjects who discontinued from the study.

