7.1.2 Assessment Time Windows

All data collected during follow-up will be displayed and analyzed according to the actual visit that the data are assigned in the eCRF.

Study discontinuation visits will be assigned to the corresponding visit if it falls within the protocol window for that visit. For example, a discontinuation visit on day 100 would be assigned to Week 13 since it falls within the -7/+14 day window for Week 13.

However, if scheduled visit data are present, then the discontinuation visit data will not be used for that visit. This will be done on a parameter level and discontinuation visit values will not be assigned to visits where the assessment was not scheduled to be taken (For example, Week 4 does not have MRI, but the discontinuation visit does; even if the discontinuation visit falls in the Week 4 window, we would not assign the MRI findings to a Week 4 visit).

Unscheduled assessments (laboratory data, imaging findings or vital signs associated with non-protocol clinical visits or obtained in investigating or managing AEs) will be included in listings but not summaries of the data. Likewise, discontinuation visit data that do not fall within a protocol-defined window or fall within a window where

scheduled visit data are already present will not be summarized, but will appear in listings.

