7.2 Efficacy Variables

The primary efficacy outcome is the change from baseline in the weekly averages of the VAS worst leg pain assessed at Weeks 1, 2, 4, 6, 13, 26, 39, and 52. Baseline is defined as the average of the 7 daily worst pain measures leading up to the randomization visit.

Key secondary outcomes include:

- Change from baseline to Week 13 in herniation volume
- Change from baseline to Week 13 in ODI score
- Change from baseline to Week 52 in average worst leg pain score during the past 24 hours over the previous 7 days, as assessed by 100 mm VAS.

Supportive outcomes include:

- Change from baseline in worst leg pain score at each time point
- Change from baseline in worst back pain score at each time point
- Change from baseline in ODI score at each time point
- Percentage of subjects with negative SLR test at each time point
- Percentage of subjects without hypoesthesia, muscle weakness or hyporeflexia at each time point
- Patient Global Impression of Change (PGIC) score at each time point
- Clinical Global Impression of Change (CGIC) score at each time point
- Change from baseline in SF-36 scores at each time point
- EQ-5D-5L (EuroQol Group 5-Dimension Quality of Life instrument, 5-level version) quality of life (QOL) score and VAS score at Week 13 and Week 52
- WPAI score at Week 13 and Week 52
- Incidence and amount of rescue medication use over 13 weeks
- Change from baseline in amount of rescue medication use at each time point
- Cumulative distribution of percentage change from baseline in worst leg pain score at Week 13 and Week 52
- Cumulative distribution of percentage change from baseline in ODI score at Week 13 and Week 52
- Responder rate by composite definition at Week 13
- Change from baseline in intervertebral disc volume at Week 13 and Week 52
- Change from baseline in herniation volume at Week 13 and Week 52
- Incidence of post-treatment surgery for LDH at the same level of investigational product injection
- Number of subjects with recurrence of LDH at Week 52

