11. CHANGES TO THE ANALYSES PLANNED IN THE PROTOCOL

The protocol-specified MI sensitivity analysis to the primary did not include consideration for subject data that is set to missing following a prohibited procedure; this has been included among the study outcomes that use the baseline distribution for imputation.

The multiple comparison algorithm has been updated to do a more straightforward serial gatekeeping approach.

The recurrence of LDH endpoint in the protocol references one of the treatment failure criteria; because this criteria was nested in other requirements that would conflict with the recurrence of LDH criteria, the text was updated to focus on only the applicable items. Additionally, surgical intervention was removed as a criteria and the symptom criteria were clarified.

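### SAP 7.3.3.5 judges recurrence of LDH at Week 52 only, without declaring that it drops the protocol's discontinuation visit, so Week 13 improvers who relapse and leave are normally not counted

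*SAP*

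**What the plan says.** Both documents label the endpoint as recurrence at Week 52 (SAP 7.2: "Number of subjects with recurrence of LDH at Week 52"). The definitions beneath that label differ in timing.

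- **Protocol 8.1.3**, condition b: "The subject does not show with any improvement of worst leg pain score, ODI score, or neurologic status at Week 52 or discontinuation visit".
- **SAP 7.3.3.5**, condition b: the same three domains (leg pain, ODI, neurologic status), judged at Week 52, with no mention of the discontinuation visit. On the denominator it says "Percentages will be reported out of subjects with any Week 52 data", and on missing data "If a subject has missing values, they will be imputed as negative outcomes".
- **SAP 7.1.2**: "Study discontinuation visits will be assigned to the corresponding visit if it falls within the protocol window for that visit". Discontinuation data outside every window are listed and not summarised.
- **SAP 11** declares that the treatment-failure reference was cut from this endpoint, and then: "Additionally, surgical intervention was removed as a criteria and the symptom criteria were clarified". It says nothing about the time point.
- **SAP Appendix 13.1** has a recurrence row with three marks. The table text is broken, but the marks follow the pattern of the lumbar-surgery row and appear to cover Week 52 and both discontinuation columns.

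SAP 7.3.3.3 reports the recurrence percentage by arm and the difference between arms.

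**The concern.** Recurrence is meant to show whether an early benefit lasts. Protocol 5.1 and 6.7.1 take subjects out of the study for poor response, and specifically for LDH surgery at any time. A subject who improves by Week 13 and then relapses badly is thus a natural candidate for early withdrawal. If recurrence is read only from Week 52 data, that subject is not counted as a non-recurrence but disappears from the percentage altogether. The protocol's definition would have captured the relapse, using data that are collected anyway: Protocol 9.2.11 obtains ODI and a neurological examination at discontinuation, and Protocol 9.5.1 has leg pain recorded daily. At stake are the reported percentage in each arm, and the arm difference if the arms differ in dropout.

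**Working it through.** **1. Can SAP 7.1.2 bring the discontinuation visit back?** Windows from the schedule of activities:

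- Week 13: Day 92 −7/+14 = Days 85 to 106
- Week 26: Day 183 ±14 = Days 169 to 197 (29 days)
- Week 39: Day 274 ±14 = Days 260 to 288 (29 days)
- Week 52: Day 365 ±14 = Days 351 to 379

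Between the Week 13 and Week 52 windows lie Days 107 to 350: 350 − 107 + 1 = 244 days. Of these, 29 + 29 = 58 map to Week 26 or Week 39, and 244 − 58 = 186 map to no visit. None maps to Week 52. One edge case: under SAP 7.3.2.1 a leg-pain average anchored at Day 351 uses Days 344 to 350, so a subject leaving just before Day 351 with at least 3 diary values in that span can have Week 52 leg pain. Hence 'normally' and 'about'.

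**2. What happens to a Week 13 improver who leaves on, say, Day 220?** The discontinuation visit is in no window and goes to listings only. There is no Week 52 leg pain, ODI or neurologic result. If Week 52 data means the endpoint's own components, the subject is in neither numerator nor denominator. Under Protocol 8.1.3 condition b, the same visit would be used.

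**3. Illustration of size.** The documents give no recurrence figure to reproduce. From them come only 160 per arm and 15% dropout (SAP 2.6). These two are mutually consistent: with difference 12, SD 30, two-sided 5% and 90% power, n = 132 per arm, and 132/0.85 rounds up to 156, near the stated 160.

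Assumed, with no support in the documents: all dropout d falls after Week 13 and before Day 351; 40% are Week 13 improvers (R); relapse is 10% in those who stay (s) and 50% in those who leave (l); every leaver is assessable at discontinuation.

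- As written: R·s
- Discontinuation visit used: (1 − d)·R·s + d·R·l
- Gap: d·R·(l − s)

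For d = 0.15: 136 stay (54.4 improvers, 5.44 relapses) and 24 leave (9.6 improvers, 4.8 relapses).

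- As written: 5.44/136 = 4.0%
- Discontinuation visit used: (5.44 + 4.8)/160 = 10.24/160 = 6.4%
- Gap: 0.15 × 0.40 × 0.40 = 2.4 points; 4.8 of 10.24 relapses (47%) go uncounted

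Varying the assumptions:

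| Change | As written | Discontinuation visit used |
|---|---|---|
| l = 10% (same as stayers) | 4.0% | 6.40/160 = 4.0% |
| l = 100% | 4.0% | 15.04/160 = 9.4% |
| d = 5%, l = 50% | 4.0% | 7.68/160 = 4.8% |
| d = 10% vs 20% by arm, l = 50% | 4.0% vs 4.0% | 5.6% vs 7.2% |

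The gap vanishes if leavers relapse no more often than stayers. In the last row the arms differ only in dropout; the rule as written shows no arm difference, whereas using the discontinuation visit shows 1.6 points.

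**The case against.** **Week 52 only may be deliberate.** The endpoint label says Week 52 in both documents, and the SAP's definition follows it. SAP 11 tells the reader that the definition was rewritten. Cutting the treatment-failure link, which included investigator-judged withdrawal, removes part of the reason for looking at the discontinuation visit. This lessens the omission but does not cure it: every change named in SAP 11 concerns which criteria apply, none concerns when they are judged, and the SAP's own schedule appears to keep the discontinuation columns. A reader might infer that the SAP leaves the timing ambiguous. It does not: its definition says Week 52. The defect is an undeclared change with a cost.

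**A stronger reading is tempting.** Target-level surgery status has Week 52 as its assessment point, and Protocol 9.5.12 says that "subjects who discontinued the study will be also followed until 52 weeks after injection". A reader might infer that this contact counts as Week 52 data and that, with missing values scored as negative, every contacted withdrawn improver becomes a recurrence whether relapsed or not. The wording does not exclude this, but the documents give it little support. The denominator sentence follows a definition built only on leg pain, ODI and neurologic status. Its example of a missing value is leg pain. SAP 11 removes surgery from this endpoint, and surgery follow-up has its own analyses (SAP 7.3.3.3 and 8.3.4). It is a reading to close off in one sentence, not the expected result. Nor do the documents support an inference that the choice was left until after unblinding.

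**The rates are invented.** That stands. The 15% dropout was set for the Week 13 comparison, and subjects who leave before Week 13 generally cannot be Week 13 improvers.

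**Conclusion.** The point holds on the text, with high confidence: the time point in condition b was narrowed without declaration, and SAP 7.1.2 does not restore the discontinuation visit on Days 107 to 350. That the omitted subjects are those most likely to have recurred is an inference from the withdrawal criteria, not an observed fact. The illustrated gap of 2.4 points (0 to 5.4 points as leaver relapse runs from 10% to 100%, from 9.4 − 4.0) shows the mechanism and its direction; it does not estimate the trial's error. The impact is low. Recurrence is an other-secondary endpoint reported descriptively, with no planned test, and it lies outside the sequence in SAP 7.3.4, so the primary and key secondary conclusions are untouched. The declared removal of surgery as a criterion is not in dispute, and neither is the use of an all-subject percentage.

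**What to change.** In SAP 7.3.3.5:

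1. Begin condition b: at Week 52, or at the discontinuation visit if it is later than the assessment used for Week 13. Use that visit's ODI and neurologic data, and the mean of the 7 diary days before it, with at least 3 values and the day exclusions of SAP 7.3.2.1.
2. Set the denominator as subjects with leg pain, ODI or neurologic data at Week 52 or at that discontinuation visit. State that surgery follow-up contact alone does not count. The existing missing-as-negative rule can then stay as one rule for everyone in the denominator, and it cannot turn a withdrawn improver with no clinical data into a recurrence.
3. Bring SAP 11 and the recurrence row of Appendix 13.1 into line with this text.

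If Week 52 only is truly intended, declare and justify it in SAP 11, correct the schedule row, and still define the denominator by the three clinical assessments.

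The cost is SAP wording and the matching table programming, with no new data. The downside is that relapse is then judged at different times in different subjects, which a table footnote should say.

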7.3.3.6 Cumulative Distribution Plots

Cumulative distribution plots of percentage change from baseline at Week 13 and Week 52 will be presented for the worst leg pain and the ODI score. Percentages will be out of all subjects, thus subjects with missing data will be counted as not having achieved a given percentage of improvement. Percentage of subjects will be on the Y axis and percentage of improvement will be on the X axis. Reference lines will mark 30% and 50% improvement.

7.3.4 Multiple Comparisons

To control family-wise error rate for multiple tests of the primary and key secondary endpoints, serial gatekeeping testing algorithm will be used.

1. The treatment effect on the primary endpoint will be evaluated at $\alpha = 0.05$.
2. If the effect on the primary endpoint is significant, the treatment effect on the key secondary endpoint of worst leg pain score at Week 52 will be evaluated using $\alpha = 0.05$.
3. If worst leg pain score at Week 52 is significant $\alpha = 0.05$, then the herniation volume at Week 13 will be tested at $\alpha = 0.05$.
4. If the herniation volume at Week 13 is significant $\alpha = 0.05$, then the ODI at Week 13 will be tested at $\alpha = 0.05$.

If at any point in the sequence an endpoint fails to meet significance at $\alpha = 0.05$, then the algorithm will be halted and the remaining tests declared non-significant regardless of their p-values. Endpoints and time points other than those above may have p-values reported, but none of these will be considered to be statistically significant.

8. SAFETY EVALUATION

8.1 Overview of Safety Analysis Methods

All safety analyses will be performed on the safety population (any subject that received an injection) and will be presented by the treatment subjects actually received. No imputation of missing values will be performed.

8.2 Adverse Events

All AEs will be coded using Medical Dictionary for Regulatory Activities (MedDRA) using the current version at the time coding is first initiated. TEAEs will be defined as any AEs that were recorded during or following the investigational product injection. Significant TEAEs will include TEAEs that result in study discontinuation. TEAEs of special interest will include TEAEs associated with hypersensitivity, imaging findings, leg pain, and back pain.

An overall display will show the number and percentage of subjects (with exact 95% CI) with TEAEs or treatment-related TEAEs that fall into the following categories: any TEAE; TEAE leading to death; serious TEAE; significant TEAE; TEAE associated with hypersensitivity; TEAE associated with imaging findings; TEAE associated with leg pain; TEAE associated with back pain. TEAEs related to study procedure will be summarized. In addition the number of subjects with TEAEs or treatment-related TEAEs will be summarized by the following:

Relationship to Study Drug	Severity	Time of First Occurrence (after injection)
Related AEs	Mild AEs	≤ 1 day
Not Related AEs	Moderate AEs	2 – 7 days
	Severe AEs	8 days – 13 weeks
		>13 weeks

Subjects experiencing AEs in more than one category will be counted in the most severe or most related group.

Detailed listings of all AEs will include severity and relationship to treatment, as well as action taken, subject outcome, and whether the AE is diagnosed or suspected COVID-19. Separate listings will be provided of subjects who experience serious TEAEs, significant TEAEs, and special interest TEAEs. Additionally, any information recorded for AEs of diagnosed or suspected COVID-19 regarding descriptions of signs/symptoms, treatments, diagnostic test results, and the resolution will be presented in a listing.

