10.1.5 Adverse Events of Special Interest

For this study, the following events will be captured as Adverse Events of Special Interest (AESI) and recorded in the eCRF:

- Injection at wrong disc level

- Discitis
- Osteomyelitis
- Hematomas
- Hypersensitivity
- Imaging findings (See Section 10.1.1 for details)
 - Disc height (disc index)
 - Vertebral body translation
 - Vertebral body angle formed by flexion
 - New Modic change
- Leg pain*
- Back pain*

*Defined as symptoms:

- associated with primary disease;
- caused by injection of investigational drug; or
- related to injection procedure.

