11.7 Safety Analyses

Treatment-emergent AEs will be defined as any AEs that were recorded during or following the investigational product injection. Significant TEAEs will include TEAEs that result in study discontinuation.

The incidence and its exact 95% confidence intervals (CIs) will be calculated by treatment group for TEAEs, serious TEAEs, significant TEAEs, and Treatment-emergent Adverse Events of Special Interest (TEAESI). The incidences of TEAEs, serious TEAEs, significant TEAEs, and TEAESI will be tabulated according to system organ class and preferred term by treatment group. The incidences of TEAEs and TEAESI will be tabulated by severity or time of occurrence for each system organ class and preferred term. Treatment-related TEAEs will also be summarized separately.

If a subject has more than 1 occurrence of the same AE, he/she will be counted only once within that preferred term in the summary tables. The most severe occurrence of an AE, as well as the most extreme relationship of the AE to the study procedures and investigational product, will be indicated in cases of multiple occurrences of the same AE.

Vital signs, laboratory assessments, imaging findings, and occurrence of post-treatment lumbar surgery will be summarized by treatment group. In addition, association between imaging findings and clinical symptoms will be assessed.

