8.2.1 Treatment-Emergent Adverse Events by System Organ Class and Preferred Term

The total number of TEAEs and the number and percentage of subjects with events will be presented by system organ class (SOC) and preferred term (PT). Subjects are counted once in each SOC and PT. Percentages will be based on the total number of treated subjects in the treatment group. SOC will be listed in the Internationally Agreed Order (found in MedDRA Data Retrieval and Presentation: Points to Consider, Release 3.2) and PTs within a SOC will be listed alphabetically.

This will be repeated for treatment-related AEs.

8.2.2 Treatment-Emergent Adverse Events by System Organ Class, Preferred Term, and Relationship/Severity

The total number of TEAEs and the number and percentage of subjects with events will be presented by SOC and PT as described above by relationship to study drug (related, not related). At each level (SOC, PT, overall), subjects will be counted as related if they have any TEAE within that level that was deemed related.

Likewise, this presentation will be repeated by severity. Subjects will be counted at the highest severity that they experience with a given level of summarization (SOC, PT, overall).

Additionally, TEAEs related to the study procedure will be displayed as above as well as broken down by severity.

8.2.3 Serious AEs, AEs leading to death, Special Interest and Significant Treatment-Emergent Adverse Events by System Organ Class and Preferred Term

The total number of TEAEs and the number and percentage of subjects with events will be presented by SOC and PT as described above for serious AEs, TEAEs leading to death, special interest TEAEs, and significant TEAEs.

TEAEs of special interest will include TEAEs associated with hypersensitivity, imaging findings, leg pain, and back pain; significant TEAEs will include TEAEs that result in study discontinuation. Specific PTs related to each of the special interest groupings will be described in the define file for the datasets.

The number of TEAEs of special interest and percentage of subjects with events will be summarized by severity and time of occurrence. Time of first occurrence will be based on time from injection and will include the following categories: ≤ 1 day; 2 – 7 days; 8 days to 13 weeks; > 13 weeks.

All the above will be repeated for treatment-related AEs only.

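### SAP 8.2 and 8.2.3 report four of the protocol's eight adverse-event categories of special interest, and SAP section 11 does not declare the reduction

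*SAP*

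**What the plan says.** **Protocol.** Section 10.1.5 states that "the following events will be captured as Adverse Events of Special Interest (AESI) and recorded in the eCRF". It then gives eight top-level entries. The first is "Injection at wrong disc level", followed by discitis, osteomyelitis, hematomas, hypersensitivity, imaging findings (with four sub-items), leg pain and back pain. Section 11.7 commits to incidence with exact 95% confidence intervals, "calculated by treatment group for TEAEs, serious TEAEs, significant TEAEs, and Treatment-emergent Adverse Events of Special Interest (TEAESI", and does not restrict the last class to part of the 10.1.5 list. It adds: "The incidences of TEAEs and TEAESI will be tabulated by severity or time of occurrence for each system organ class and preferred term".

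**SAP.** Section 8.2 states that "TEAEs of special interest will include TEAEs associated with hypersensitivity, imaging findings, leg pain, and back pain", and 8.2.3 repeats the same four. The overall display in 8.2 has exact 95% intervals and rows for any TEAE, TEAE leading to death, serious TEAE, significant TEAE and each of those four groupings. Section 8.2.3 provides tables "presented by SOC and PT as described above for serious AEs, TEAEs leading to death, special interest TEAEs, and significant TEAEs", and special-interest tables by severity and by time since injection. It leaves the preferred terms for each grouping to the dataset define file.

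**Treatment-emergence.** Protocol 10.1.1 covers onset, or an increase in severity, after administration. Protocol 11.7 and SAP 8.2 cover events recorded at or after the injection and do not mention worsening.

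**The concern.** Showing whether the product is safe and well tolerated is a secondary objective (protocol 2.2). The protocol singled out eight event types for separate reporting. The four that the SAP leaves out are wrong-level injection and the infection and bleeding events, and protocol 1.2.1.5 names bleeding and infection among the risks of the injection procedure. A reader who takes the special-interest outputs as complete against the protocol would not see these four types in the display or tables and would not be told that they had been removed. The database and the outputs could also disagree: the eCRF has a Yes/No special-interest item (protocol 9.6.1), so a discitis flagged Yes would fall outside the SAP's special-interest tables.

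The treatment-emergence wording raises a smaller issue. AE recording starts at consent (protocol 10.2), so an event that begins in screening and worsens after injection is treatment-emergent under 10.1.1 but not clearly so under 11.7 and SAP 8.2.

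**Working it through.** The check is a comparison of lists; no alpha, power or sample size enters.

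**1. The two lists**

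| Protocol 10.1.5 | SAP 8.2 and 8.2.3 | Row in SAP 8.2 display |
|---|---|---|
| Injection at wrong disc level | no | no |
| Discitis | no | no |
| Osteomyelitis | no | no |
| Hematomas | no | no |
| Hypersensitivity | yes | yes |
| Imaging findings | yes | yes |
| Leg pain | yes | yes |
| Back pain | yes | yes |

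Protocol 8, SAP 4, missing 8 − 4 = 4, which is 4/8 = 50% of top-level categories. If the four imaging sub-items are counted singly, the protocol has 7 + 4 = 11 items and 4/11 = 36% are missing. Either way the same four types are absent, and the SAP adds none.

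**2. Is the cut declared?** SAP section 11 covers three topics: the multiple-imputation sensitivity analysis, the multiplicity procedure and the definition of recurrence. None concerns adverse events.

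**3. Which outputs are affected?** The overall display and the special-interest tables (by SOC and preferred term, by severity, by time of occurrence, and their treatment-related repeats). The special-interest listing is probably affected too, but the SAP does not say whether it is driven by the eCRF flag or by the preferred-term groupings.

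**4. Exact intervals.** Protocol 11.7 names four classes: TEAEs, serious, significant and special-interest. The SAP display has a row for each of the first three as a class. For the fourth it has exact intervals for the four named groupings but no row for any special-interest event. If 11.7 means the class as a whole, one row is missing; if it means each grouping, the shortfall is the four omitted groupings.

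**5. Time of occurrence.** SAP 8.2 gives time of first occurrence for all TEAEs in aggregate ("In addition the number of subjects with TEAEs or treatment-related TEAEs will be summarized by the following"). SAP 8.2.2 breaks the SOC and preferred-term table down by relationship and then severity ("Likewise, this presentation will be repeated by severity"), not by time. Protocol 11.7 joins severity and time with *or*. Read as a choice, the SAP complies; read as both, a table is missing.

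**6. What a restored row would show.** Assume that all 160 planned subjects per arm are injected. With 0 events the exact two-sided 95% upper limit is 1 − 0.025^(1/160) = 2.28%. With 1 event the interval is 0.02% to 3.43%, and with 2 events it is 0.15% to 4.44%.

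**7. Treatment-emergence**

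| | Onset during injection | Onset after | Worsening after |
|---|---|---|---|
| Protocol 10.1.1 | not stated | yes | yes |
| Protocol 11.7 | yes | yes | not stated |
| SAP 8.2 | yes | yes | not stated |

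The SAP follows 11.7, so the conflict lies inside the protocol. It chiefly concerns AEs with onset between consent and injection, planned as no more than 4 weeks (Table 1, note h). The documents give no basis for sizing it.

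**The case against.** **The list may be open-ended.** The SAP says that special-interest events will *include* the four. Against this, the same verb introduces significant TEAEs, where it plainly defines; the list appears twice; the display has exactly those four special-interest rows; and preferred terms are planned for each grouping. A programmer would build four groupings. The point survives only for the listing, whose source the SAP does not state.

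**The events are reported elsewhere.** This stands. A reader might infer that the omitted types drop out of safety reporting. The documents do not support that: treatment-emergent cases appear in the general SOC and preferred-term tables and the AE listings, and in the procedure-related, serious or significant TEAE tables where they qualify.

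**The exact intervals are there.** A reader might infer that the SAP gives no exact interval for special-interest events. It gives one for each of the four named groupings. The missing pooled row departs from protocol 11.7 on one reading only.

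**The time table was optional.** A reader might infer that the SAP drops a promised time-by-SOC and preferred-term table for all TEAEs. Because 11.7 says severity *or* time, that is one of two readings and is not counted as an established departure.

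**The treatment-emergence wording is harmless, or not the SAP's doing.** A reader might infer that the SAP changed the definition; it did not. *Recorded* could also cover a worsening entered as an AE after injection. That depends on eCRF instructions which the documents do not show, so the inconsistency stands but its effect is uncertain.

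**Conclusion.** The main point holds with high confidence. The SAP's special-interest definition omits four of the eight top-level categories in protocol 10.1.5, and section 11 does not say so. As written, the overall display and special-interest tables would be incomplete against protocol 10.1.5 and 11.7; the listing probably would be too. This rests on reading the SAP list as a definition, which its repetition and the display rows support.

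The consequence is confined to how safety is presented. No event, alpha, power or efficacy result is affected. It should be corrected, but it does not threaten the trial's conclusions.

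The treatment-emergence mismatch is a separate, lower-rated point held with medium confidence. It is internal to the protocol, and its effect cannot be sized.

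**What to change.** **Special-interest events.** List all eight protocol 10.1.5 categories in SAP 8.2 and 8.2.3. Carry them into the overall display with exact 95% intervals, the special-interest tables and the listing. Add a row for any special-interest event, and state whether the listing uses the eCRF flag or the preferred-term groupings. If the reduction is intended, declare and justify it in SAP section 11. It would also help to say which reading of severity *or* time in protocol 11.7 applies to all TEAEs.

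*Cost:* SAP wording, a few table lines, and preferred-term groupings for four more categories in the define file. The groupings are needed because the eCRF item is only Yes/No; the same work is already planned for the other four.

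**Treatment-emergence.** Use one definition in protocol 10.1.1, protocol 11.7 and SAP 8.2: onset, or worsening in severity, during or following the injection.

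*Cost:* wording in three places. Applying the worsening clause also needs a rule for how worsening of a pre-injection event is entered, because protocol 9.6.1 lists one severity item per AE. If the eCRF instructions already contain such a rule, nothing more is needed.
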